Correlation of Spinopelvic Movement with
Lateral Radiographs to Assess Spine Motion
Prior to Total Hip Arthroplasty.

NCT05117229

6/21/2021

6-21-2021

Correlation of Spinopelvic Movement with Lateral Radiographs to Assess Spine Motion Prior to Total Hip Arthroplasty.

Design: Prospective pilot study

Aims:

- 1) To evaluate the correlation between a novel pelvic MetaWear sensor that assesses spinopelvic motion with lateral sit-to-stand radiographs.
- 2) To evaluate the relationship between a novel pelvic sensor with pelvic tilt, sacral slope, and lumbar lordosis.

Background: Spinopelvic relationships are increasingly recognized as an important part of total hip arthroplasty and determinant of stability after THA. A number of recent papers in the literature have correlated stiffness of the spinopelvic parameters and the potential risk of total hip arthroplasty dislocation. Most commonly, assessment is performed with lateral sit-to-stand radiographs where changes of less than 10 degrees in sacral slope have been described as stiff spines and could represent patients at increased risk of instability. Given the dynamic nature of the hip/spine biomechanics, which is further influenced by relative stiffness of the hip/spine complex, it remains to be determined how the patient's actual motion impacts these radiographic parameters. MetaWear sensors positioned on the pelvis can potentially provide meaningful spinopelvic motion parameters and could eliminate the need for additional radiation needed to obtain lateral radiographs. The correlation between the MetaWear sensor obtained spinopelvic motion and radiographic data obtained from the more traditional lateral sit to stand radiographs is needed.

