We will prospectively evaluate 40 patients presenting for surgery at the Division of Hip and Knee Arthroplasty at Mayo Clinic. An assessment of pelvic motion will be obtained through MetaWear sensors. Data capture will then be verified by the Research Coordinator. Preliminary data shows in 2019, OrthAlign, Inc. conducted an internal study utilizing one sensor device strapped to the femur and one sensor device attached to the skin by the patient's sacrum using the same devices and adhesive in the proposed study. The study included 10 employees with no prior knowledge of everyone pelvic or spinal mobility. A physical therapist conducted the study according to the protocol consistently across all individuals. Measurements were taken while sitting, standing, and leaning forward. All intended data was able to be collected with no adverse events. Across the patient population, the average change in pelvic mobility between sitting and standing was 11.86° with a standard deviation of 6.99° , minimum of -1.07° and a maximum of 28.25° . In a study using radiographs, Seyler et al.¹ found an average of 19.2° , standard deviation of 9.9° , min of 1.6° , maximum of 37.5° in change in pelvic tilt across 24 subjects. Nine total measurements were taken per individual. Three sets of measurements were taken. Each set contained three measurements under the same conditions. Between datasets, the sensors were removed and

re-applied. The standard deviation within and across datasets were calculated for each patient. The standard deviation within datasets was just under 3.0° and the standard deviation across datasets was 3.2° . These standard deviations were compared to radiographs study data². The study showed standard deviations between approximated 2.7° and 3.5° for radiograph measurements of sacral slope and APP angle during standing and sitting positions. Therefore, we concluded our study produce feasible pelvic range of motion results between sitting and standing positions with repeatability and reproducibility comparable to radiograph technology.

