Following collection and annotation of all data, a password protected spreadsheet on a departmental-secured server will be shared with a statistician from the Division of Biomedical Statistics and Informatics. Categorical data will be tabulated as counts and percentages and continuous data as means and ranges with standard deviations and confidence intervals as appropriate. Correlations and means between radiographic parameters obtained from lateral radiographs will be calculated and correlated with spinopelvic motion obtained through the MetaWear sensors. Sensitivity analysis or adjusted analyses will be performed for age, sex, and hip pathology as deemed appropriate by the statistician.

Device Description:

Each device is a MetaWear, MotionC wearable sensor. The device contains a circuit board with a MEMS gyroscope, accelerometer, magnetometer, barometric pressure, and light ambient sensor. Not all sensors are used for this study. The circuit is encased in a plastic housing. Real-time communication to a tablet is achieved via BluetoothLE wireless communication. The device is FCC, CE, IC and RoHS compliant.

Adverse Events:

Adverse events will be monitored and reported to the PI who will make the data available to the DSMB. However, we do not anticipate any adverse event occurring with the use of such sensor technology. The only adverse even would be associated with sensitivity to adhesive tape during the MetaWear sensor placement.

References:

¹ Sutter EG, Wellman SS, Bolognesi MP, Seyler TM. “A Geometric Model to Determine Patient-Specific Cup Anteversion Based on Pelvic Motion in Total Hip Arthroplasty.” *Adv Orthop.* 2019 May 2;2019:4780280. doi: 10.1155/2019/4780280. PMID: 31186967; PMCID: PMC6521545.

² J.-Y. Lazennec, M.-A. Rousseau, A. Rangel, M. Gorin, C. Belicourt, A. Brusson, Y. Catonné

“Pelvis and total hip arthroplasty acetabular component orientations in sitting and standing positions: Measurements reproducibility with EOS imaging system versus conventional radiographies”

Revue de Chirurgie Orthopédique et Traumatologique, Volume 97, Issue 4, June 2011, Pages 375-383

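### Correlation is the only sensor-to-film comparison the protocol names; adding a paired difference and limits of agreement for one like-for-like angle would be a cheap improvement

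*Protocol*

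**What the plan says.** Aim 1 reads: "To evaluate the correlation between a novel pelvic MetaWear sensor that assesses spinopelvic motion with lateral sit-to-stand radiographs". The Background closes in the same vein: "The correlation between the MetaWear sensor obtained spinopelvic motion and radiographic data obtained from the more traditional lateral sit to stand radiographs is needed". Methods again speaks of correlations between sensor data and radiographs, and Statistical analysis describes a pilot to correlate PI, PT, SS and LL with sensor motion. The analysis text itself is: "Correlations and means between radiographic parameters obtained from lateral radiographs will be calculated and correlated with spinopelvic motion obtained through the MetaWear sensors". It also promises means, ranges, SDs and confidence intervals for continuous variables, and adjusted or sensitivity analyses for age, sex and hip pathology.

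No difference between sensor and film within a patient is named anywhere in the protocol. The interobserver statistics under Post-radiographic evaluation compare film readers with each other.

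The Background also gives a motive that goes beyond association: the sensor "could eliminate the need for additional radiation needed to obtain lateral radiographs".

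The sensor output is called spinopelvic motion in some places and pelvic motion or pelvic mobility in others. None of the four radiographic parameters is marked as its direct counterpart.

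**The concern.** Whether a sensor could stand in for a film depends on how many degrees apart the two readings are in the same patient. A correlation coefficient does not report that. It is unchanged if the sensor reads a constant amount too low or compresses the range. It also depends on how varied the patients are, which the age quota (20, 10 and 10 patients) helps to set. A high r from this pilot could therefore be read as support for dropping films when the degree-by-degree disagreement has not been looked at.

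The preliminary data already lean that way. They call the sensor's repeatability comparable to that of radiographs, but this sets each method's own scatter side by side. It does not compare the two methods in the same people.

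The films are taken with the sensors in place, so the paired readings will exist. What is missing is a definition of the angle and a few lines of analysis.

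**Working it through.** **Is there a planned figure to reproduce?** No. The protocol states that no power analysis was done and gives no target r, alpha or acceptable difference. The only arithmetic is the age quota, 20 + 10 + 10 = 40, which agrees with the total.

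**Inputs**
- Sensor sit-to-stand change: mean 11.86°, SD 6.99°, 10 employees (preliminary data).
- Radiographic change in pelvic tilt: mean 19.2°, SD 9.9°, 24 subjects of a cited study (preliminary data).
- Number of pairs: at most 40.
- r between sensor and film: not in the document. Assumed 0.9, with 0.7 and 0.8 for comparison.

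**Step 1: offset and scale.** For any a > 0, corr(aX + b, Y) = corr(X, Y). In a simulated sample of 40, r was 0.915 both before and after the sensor value was multiplied by 0.7 and lowered by 7.34°.

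**Step 2: what a given r leaves open.** SD of differences = sqrt(s1² + s2² − 2·r·s1·s2), and limits = bias ± 1.96 × that SD. At r = 0.9:
- both SDs 6.99°: SD of differences 3.13°, limits ±6.1°
- both SDs 9.9°: 4.43°, ±8.7°
- 6.99° and 9.9°: 4.72°, ±9.3°

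With SDs of 6.99° and 9.9°, r = 0.8 gives ±11.8° and r = 0.7 gives ±13.9°.

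**Step 3: dependence on patient spread.** With equal SD S in both methods, r = 1 − d²/(2S²), where d is the SD of differences. Hold d at 4.43°. Then S = 9.9° gives r = 1 − 19.60/196.02 = 0.90, and S = 6.99° gives r = 1 − 19.60/97.72 = 0.80. The disagreement in degrees is the same and r differs by 0.10.

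**Step 4: could the planned summaries supply the answer?** Mean difference = difference of the two means. The SD of differences follows from the two SDs and r, as in Step 2. This works only if both variables are the same angle, their signs are aligned, r is Pearson's, and means, SDs and r come from the same patients. The protocol fixes none of these four. The preliminary values are signed ("minimum of -1.07° and a maximum of 28.25"), so the sign convention is a live question.

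**Step 5: precision of the addition.** The 95% CI half-width is t(n−1)/√n for the bias and t(n−1)·sqrt(1/n + 1.96²/(2(n−1))) for each limit, in units of the SD of differences:
- n = 40: 0.32 and 0.55
- n = 36 (assumed 10% loss): 0.34 and 0.58
- n = 32 (assumed 20% loss): 0.36 and 0.62

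With SDs of differences of 3.13° to 4.72° and 40 pairs, this is about ±1.0° to ±1.5° for the bias and ±1.7° to ±2.6° for each limit.

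**The case against.** The strongest reply is that nothing here is wrong. The study is a pilot of correlation, its aim says so, and its analysis delivers it. Replacing films appears once, in the Background, as a hedged possibility; no aim or success criterion depends on it. A statistical analysis plan that is not at hand may add agreement statistics. All of this stands, and it is why the point is an improvement only.

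It is also true that the planned analysis is not uninformative about replacement. A low r would speak against it, and the planned means and SDs could be combined with r if the conditions in Step 4 were met. What remains is that those conditions are open.

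Three stronger readings are tempting, and the document does not support them:
- **The sensor under-reads films by about 7°.** The gap 11.86 − 19.2 = −7.34° compares different people and possibly different angles. It is not evidence of bias.
- **Limits of agreement can be computed from the repeatability SDs.** The protocol reports "The standard deviation within datasets was just under 3.0° and the standard deviation across datasets was 3.2" degrees for the sensor, and 2.7° to 3.5° "for radiograph measurements of sacral slope and APP angle during standing and sitting positions". Adding these variances assumes independent errors. Part of the sensor scatter may be true variation in how a person sits and stands; with films taken while the sensors are worn, that part could be shared and cancel. The film SDs also come from another study.
- **The preliminary work used a different sensor set-up.** It had "one sensor device strapped to the femur and one sensor device attached to the skin" near the sacrum, whereas Methods speaks of a sensor on the pelvis. But placement is shown in a figure that is not available here, the sacrum is part of the pelvis, and the protocol says the devices were the same. A different set-up is possible, not established.

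**Conclusion.** The point holds as a cheap improvement. The protocol names correlation, with separate descriptive summaries, as its only sensor-to-film comparison. That answers the stated aim. On its own it says little about the hope of sparing films, and the route from the planned summaries to a paired difference is not secured because no like-for-like angle is fixed.

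The size is illustrative: an r of 0.9 is compatible with limits of agreement of about ±6.1° to ±9.3° around any bias. This rests on an assumed r, on SDs from different people and on approximately normal differences. The protocol gives no acceptable limit to judge these against. Its 10° change in sacral slope describes a stiff spine; it is not a tolerance for disagreement between methods.

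**What to change.** Leave Aim 1 as worded and add to the statistical section:

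1. Define the sensor's sit-to-stand rotation in degrees so that it matches the radiographic sit-to-stand change in sacral slope, or in pelvic tilt with signs aligned.
2. For that pair, report beside r the mean paired difference (sensor minus radiograph) with 95% CI, Bland-Altman 95% limits of agreement with CIs, and a check of difference against mean. State the number of complete pairs, since unusable films or failed tracking can remove some.
3. If no common angle can be defined, report correlation only and state that agreement was not assessed.

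Correlations with the other radiographic parameters can stay as planned.

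**Cost.** Slightly more analysis on the same patients, films and recordings. The result may look less favourable than r alone, and precision is modest: with 40 pairs, about 0.32 SD of the differences either side for the bias and 0.55 SD for each limit.
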